7.23.1.3 IDDD-related Adverse Events

IDDD ADVERSE EVENTS

Examples of AEs related to use of the IDDD include, but are not limited to, the following: device failure, device malfunction, incorrect connection of IDDD components, erosion of the portal/catheter through the skin, fibrin sheath formation around the catheter tip, hematoma, implant rejection, migration of the portal/catheter, occlusion of the portal/catheter, portal site or subcutaneous tract infection. The device may also need to be replaced or repaired as needed. A list of the more common IDDD AEs is included in [Appendix 3](#).

If the patient is admitted to the hospital in association with an IDDD event (eg for subsequent revision or replacement) the surgery will be recorded as a SAE.

DEVICE SURGICAL PROCEDURE-RELATED ADVERSE EVENTS

Examples of AEs related to surgical procedures include, but are not limited to, the following: IDDD implant/explant, IDDD adjustment, full revision, partial revision, IDDD removal, and delayed re-implantation after previous IDDD removal.

IT ADMINISTRATION PROCESS ADVERSE EVENTS

In studies that include administration of investigational drug with an IDDD, potential AEs related to the IT Administration process include AEs that are caused by anesthesia during drug administration, drug administration issues (eg, extravasation during infusion or hematoma due to Huber needle), etc.

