7.23 Adverse Events

7.23.1 Definitions of Adverse Events and Serious Adverse Events

7.23.1.1 Adverse Event

An AE is any noxious, pathologic, or unintended change in anatomical, physiologic, or metabolic function as indicated by physical signs, symptoms, or laboratory changes occurring in any phase of a clinical study, whether or not considered study drug-related. This includes an exacerbation of a pre-existing condition. Once the informed consent is signed and dated, any adverse event prior to the start of study drug must be reported.

AEs include:

- Worsening (change in nature, severity, or frequency) of conditions present at the onset of the study
- Intercurrent illnesses
- Drug interactions
- Events related to or possibly related to concomitant medications
- Abnormal laboratory values (this includes significant shifts from baseline within the range of normal that the Investigator considers to be clinically important)
- Clinically significant abnormalities in physical examination, vital signs, and weight

Throughout the study, the Investigator must record all AEs on the AE eCRF, regardless of the severity or relationship to study drug. The Investigator should treat patients with AEs appropriately and observe them at suitable intervals until the events stabilize or resolve. AEs may be discovered through observation or examination of the patient, questioning of the patient, complaint by the patient, or by abnormal clinical laboratory values.

In addition, AEs may also include laboratory values that become significantly out of range. In the event of an out-of-range value, the laboratory test should be repeated until it returns to normal or can be explained and the patient's safety is not at risk.

All AEs should be recorded with causality assessment.

The information presented below is intended to provide issues to consider for AEs associated with intrathecal injections of HGT-1410. In general, these AEs can be classified as follows:

- Adverse events due to systemic exposure to HGT-1410 caused by the drug diffusion from the CSF to the peripheral circulation;
- Adverse events related to the direct delivery of HGT-1410 to the intrathecal CSF space and meninges, and subsequent diffusion into brain parenchyma, via an intrathecal route
- IDDD-related AEs

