7.23.1.4 Serious Adverse Event

1. A serious AE (SAE) is any AE occurring at any dose of investigational drug or at any procedure that results in any of the following outcomes:

- Death
- Is life-threatening
- Requires inpatient hospitalization
- Requires prolongation of existing hospitalization
- A persistent or significant disability or incapacity
- A congenital anomaly or birth defect

Important medical events that may not result in death, be life-threatening, or require hospitalization may be considered an SAE when, based upon appropriate medical judgment, they may jeopardize the patient and may require medical or surgical intervention to prevent one of the outcomes listed in this definition. Examples of such medical events include allergic bronchospasm requiring intensive treatment in an emergency room or at home, blood dyscrasias or convulsions that do not result in inpatient hospitalization. Hospitalizations, which are the result of elective or previously scheduled surgery for pre-existing conditions, which have not worsened after initiation of treatment, should not be classified as SAEs. For example, an admission for a previously scheduled ventral hernia repair would not be classified as an SAE; however, complication(s) resulting from a hospitalization for an elective or previously scheduled surgery that meet(s) serious criteria must be reported as SAE(s). *Furthermore, this does not apply to device failures resulting in scheduled surgical revisions, which should be reported as SAEs.*

2. Unanticipated Adverse Device Effect (UADE) - Any serious adverse effect on health or safety or any life-threatening problem or death caused by, or associated with, a device, if that effect, problem, or death was not previously identified in nature, severity, or degree of incidence in the investigational plan or application (including a supplementary plan or application), or any other unanticipated serious problem associated with a device that relates to the rights, safety, or welfare of patients. (21CFR812.3[s] or other regulatory requirements, as applicable).

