8.2.1.2 Day 2 (± 2 days) Assessments and Administration of HGT-1410

Patients may be discharged from the clinical site 4 hours after dosing, if deemed stable by the Investigator.

- Physical examination
- ECG (performed following IT study drug injection)
- Vital signs
- CSF sample collection (obtained prior to IT study drug injection)
- HGT-1410 IT injection (Day 2 ± 2 days)
- Neurological examination
- Concomitant medications, therapies, and procedures
- AE assessments

The neurological exam should not occur sooner than 4 hours after study drug administration or before the patient has fully recovered from any anesthesia administered for the dosing, whichever occurs later.

8.3 End of Study/Early Termination Procedures: Month 55

Patients who complete the study or who discontinue prior to the end of the study, will have EOS assessments performed 30 (± 7 days) after their last dose of HGT-1410.

Patients who discontinue or are withdrawn prior to study completion will be asked to participate in the EOS procedures at the time of discontinuation. Participation in these EOS procedures will be strongly encouraged, but is voluntary for those patients electing to discontinue from the study. Note: Patients will have the IDDD removed when they discontinue from the study, unless the patient is continuing to receive treatment through another mechanism (eg, expanded access, commercially available).

- Physical examination
- Height and weight
- Head circumference
- Visual and hearing assessment
- ECG
- Vital signs
- Hematology
- Serum chemistries
- Urinalysis
- Urine heparan sulfate and heparan sulfate derivatives
- Plasma and serum heparan sulfate and heparan sulfate derivatives
- Anti-rhHNS antibody testing
- ABR (unless performed at Month 54)
- MRI of the head (unless performed at Month 54)
- CSF sample collection (unless performed at Month 54)
- Neurological examination
- Full neurodevelopmental testing, including VABS-II
- Children's Sleep Habits Rating Scale
- Child health questionnaire-50
- Child health questionnaire-87
- Infant toddler QoL Questionnaire
- Concomitant medications, therapies, and procedures
- AE assessments
- X-ray of device, if the patient is to continue to receive intrathecal HGT-1410 beyond the end of the study

All patients who discontinue the study early will have their IDDD removed.

Patients who withdraw or discontinue after having received fewer than 3 IT injections will not need to complete the EOS visit.

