10.6 Efficacy, Safety, and Pharmacodynamic Evaluations

10.6.1 Primary Analyses

10.6.1.1 Safety Analysis

In general, safety assessments will be based on all assessments post-baseline. The assessment of safety will be based primarily on the frequency of AEs, and on the frequency of clinically notable abnormal vital sign and laboratory values. Changes from baseline will be calculated by subtracting the baseline value from the post-baseline value.

All enrolled patients who had an IDDD surgical procedure and/or received administration of HGT-1410 will be included in the safety analysis.

Adverse events will be recorded throughout the study and at early termination. Adverse events and medical conditions will be coded using the Medical Dictionary for Regulatory Activities (MedDRA).

Adverse events will be summarized by presenting, for each dose group, the number and percentage of patients having any AE, having an AE in system organ class, and having each individual AE. In addition, those events which resulted in death or were otherwise classified as serious will be presented in a separate listing. The incidence of treatment-emergent adverse events, defined as all AEs from the time of the surgery for IDDD implantation to the last follow up contact, ie, 30 days after the last HGT-1410 administration, (new or worsened from baseline) will be summarized by system organ class, severity, type of adverse event and relationship to trial medication/procedure.

Treatment-emergent AEs deemed related to HGT-1410 administration will be summarized separately.

IDDD, and procedure-related AEs will be summarized within system organ class by preferred term. IDDD and procedure-related AEs will be tabulated by severity (mild, moderate, severe) and degree of relatedness. Separate tabulations will be provided for adverse events related to the IDDD, device surgical procedure (including post-implant infections) and IT administration process. These summaries will be presented by device and overall, as appropriate.

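### Section 7.23.1.3 lists device operations as adverse events, and with 7.23.1.4 it leaves open whether the failure or the surgery is the reported SAE

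*Protocol*

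**What the plan says.** Section 7.23.1.1 defines an AE as "any noxious, pathologic, or unintended change in anatomical, physiologic, or metabolic function", shown by signs, symptoms or laboratory changes.

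Section 7.23.1.3 has three groups of device-related AEs. The group for device surgery opens with "Examples of AEs related to surgical procedures include, but are not limited to, the following" and then names "IDDD implant/explant, IDDD adjustment, full revision, partial revision, IDDD removal, and delayed re-implantation after previous IDDD removal". Every item is an operation.

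On seriousness, 7.23.1.3 has this rule for anyone "admitted to the hospital in association with an IDDD event (eg for subsequent revision or replacement) the surgery will be recorded as a SAE". Section 7.23.1.4 exempts hospitalizations for elective or previously scheduled surgery for pre-existing conditions from SAE status, and then adds that "this does not apply to device failures resulting in scheduled surgical revisions, which should be reported as SAEs".

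Section 10.6.1.1 feeds these records into the safety tables: "Separate tabulations will be provided for adverse events related to the IDDD, device surgical procedure (including post-implant infections) and IT administration process". The summaries are by device and overall, as appropriate.

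**The concern.** A site that follows the list as written enters an AE because an operation took place, whether or not anything went wrong. Some of these operations are steps of the protocol. Appendix 1 schedules IDDD removal at Month 54 or at the end-of-study visit, and section 8.3 adds "All patients who discontinue the study early will have their IDDD removed". After Amendment 4, any replacement is a SOPH-A-PORT implant.

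AEs are the first primary endpoint in section 3.1, and the SOPH-A-PORT was introduced because it was expected to cause fewer complications than the PORT-A-CATH. A by-device procedure-AE percentage that includes the implant operation itself says little about that expectation, even descriptively.

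The SAE wording raises a second question. For one failed catheter replaced in hospital, the protocol does not say whether the report is the failure, the operation or both. These are rules for what sites record and report, so an analysis plan written later cannot fully repair them.

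**Working it through.** The protocol states no AE or SAE rate to reproduce, so the check sets the sections side by side and shows how far the counts can move.

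**1. Is the list really a list of AEs?** The other two groups in 7.23.1.3 use the same form and name true events: occlusion, migration and infection for the device; extravasation and hematoma for the administration process. Only the surgical group names operations. Appendix 3 already holds complication terms for implantation and access, such as CSF leak, bleeding, implant-site infection and wound dehiscence. The list therefore conflicts with 7.23.1.1 and differs from the groups beside it.

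**2. SOPH-A-PORT patients.** Sections 10.1 and 10.3 base the SOPH-A-PORT analyses on patients who had the implant procedure performed. If the implant is an AE, then for *m* such patients the incidence is *m*/*m* = 100% by construction, with no harm needed.

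**3. All patients.** Inputs: maximum N = 12 (section 10.2). Assumptions: no patient is harmed by device surgery, no other listed operation takes place, planned removals fall inside the reporting window, and *r* of the 12 patients have one (*r* is not in the protocol). Exact (Clopper-Pearson) 95% intervals:

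- complications only: 0/12 (0 to 26.5%);
- listed operations counted, *r* = 0: 0/12 (0 to 26.5%);
- *r* = 6: 6/12 (21.1 to 78.9%);
- *r* = 12: 12/12 (73.5 to 100%).

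The whole movement comes from planned removals.

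**4. Seriousness rules.**

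- 7.23.1.3: the trigger is admission in association with an IDDD event; the unit is the surgery.
- 7.23.1.4: the trigger is a failure resulting in scheduled revision, with admission not named in the clause; the unit is the failure.

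Assume 6 failures that need scheduled revision, a share *a* of them admitted (neither figure is in the protocol):

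- 7.23.1.3 alone: 6*a* SAEs, which is 0, 3 or 6 at *a* = 0, 0.5 or 1;
- 7.23.1.4 read without an admission condition: 6 at every *a*;
- failure and surgery both recorded, on that reading: 6 + 6*a* = 6, 9 or 12.

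The first two agree in number only at *a* = 1. Even then one reports the operation and the other the failure.

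**The case against.** The best defence is that examples do not define an AE; 7.23.1.1 does. That section offers the device categories as matters to consider, and a note says the examples are theoretical or drawn from literature. Table 7-4 and section 7.23.5.2 treat device surgery as something to which an AE may be related. The list may have been meant as the procedures from which AEs can arise. That intention is plausible, but it is not what the sentence says.

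Four stronger conclusions are tempting, and the protocol does not support them.

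- *The tables measure planned surgery instead of harm.* Section 10.6.1.1 expressly includes post-implant infections and summarizes these AEs by preferred term, so a removal would be its own row and would not hide an infection. Section 10.6.2.1 reports failures and malfunctions separately with a rate and 95% confidence interval, although its detailed summary is for SOPH-A-PORT patients.
- *Procedure-AE incidence will approach 12/12.* Patients arrive already implanted from HGT-SAN-055, and section 7.13.4 waives removal for those who continue treatment by another mechanism. 12/12 is only the literal maximum.
- *The two seriousness rules contradict each other.* Section 7.23.1.3 says if, not only if. The clause in 7.23.1.4 is an exception to a hospitalization exemption and can be read as assuming admission, which would align the triggers. It would not align the unit.
- *Double recording inflates SAE incidence.* No section tells sites to file both. Section 10.6.1.1 counts patients for AE incidence and puts serious events in a listing, so two records in one patient do not change patient-level incidence.

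**Conclusion.** The point holds as a defect of definition and recording. The surgical list in 7.23.1.3 conflicts with 7.23.1.1. Followed literally, it makes the procedure-AE figure 100% by construction in SOPH-A-PORT patients and lets planned removals move the all-patient figure within 0/12 to 12/12. The effect is a mixture: complications remain in the tables, but the category total cannot be read as a complication rate. This depends on sites applying the list as written and on the number of planned removals, which is unknown.

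The SAE wording is unaligned, not strictly contradictory. The reported unit differs between 7.23.1.3 and 7.23.1.4, and the trigger differs only if the 7.23.1.4 clause is read without admission. What suffers is the number and identity of SAE records, which may also vary with local admission practice. No formal device comparison is affected, because section 10.1 plans none. The change should be made, since it concerns a primary endpoint and costs little.

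**What to change.** - In 7.23.1.3, replace the operations in the surgical group with complications of those operations, using terms already in Appendix 3.
- State there that a planned implant, revision or removal is a procedure, or the action taken for an underlying event, and is not in itself an AE.
- Reconcile 7.23.1.3 with 7.23.1.4 so that one trigger and one reported unit apply to a device failure, and say explicitly whether the associated surgery is a separate report.

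The cost is wording in two sections, an eCRF completion note and re-review of device events already entered. Treatment and visits do not change, and expedited reporting of device failures can continue.

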7.23.1.4 Serious Adverse Event

1. A serious AE (SAE) is any AE occurring at any dose of investigational drug or at any procedure that results in any of the following outcomes:

- Death
- Is life-threatening
- Requires inpatient hospitalization
- Requires prolongation of existing hospitalization
- A persistent or significant disability or incapacity
- A congenital anomaly or birth defect

Important medical events that may not result in death, be life-threatening, or require hospitalization may be considered an SAE when, based upon appropriate medical judgment, they may jeopardize the patient and may require medical or surgical intervention to prevent one of the outcomes listed in this definition. Examples of such medical events include allergic bronchospasm requiring intensive treatment in an emergency room or at home, blood dyscrasias or convulsions that do not result in inpatient hospitalization. Hospitalizations, which are the result of elective or previously scheduled surgery for pre-existing conditions, which have not worsened after initiation of treatment, should not be classified as SAEs. For example, an admission for a previously scheduled ventral hernia repair would not be classified as an SAE; however, complication(s) resulting from a hospitalization for an elective or previously scheduled surgery that meet(s) serious criteria must be reported as SAE(s). *Furthermore, this does not apply to device failures resulting in scheduled surgical revisions, which should be reported as SAEs.*

2. Unanticipated Adverse Device Effect (UADE) - Any serious adverse effect on health or safety or any life-threatening problem or death caused by, or associated with, a device, if that effect, problem, or death was not previously identified in nature, severity, or degree of incidence in the investigational plan or application (including a supplementary plan or application), or any other unanticipated serious problem associated with a device that relates to the rights, safety, or welfare of patients. (21CFR812.3[s] or other regulatory requirements, as applicable).

7.23.2 Device-Associated Definitions

7.23.2.1 Device Revision (Partial and Full)

Partial device revision: surgical revision/replacement of one or more component(s) of the device; other component(s) of the original device remain implanted and are not affected (eg, port revision).

Full device revision: the device is removed (explanted) in its entirety and a completely new device is implanted.

7.23.2.2 Device Malfunction

The device does not perform as intended, based on the description in the device's IFU, but does not require either a partial or full device revision.

7.23.2.3 Device Failure

The device irreversibly fails to perform as intended and requires either a partial or full device revision or removal.

7.23.3 Classification of Adverse Events and Serious Adverse Events

The National Cancer Institute Common Terminology Criteria for Adverse Events (NCI CTCAE) version 3.0 grading scale should be referenced when assessing the severity of an AE (see [Appendix 6](#)). If an AE is not described in the NCI CTC, the severity should be recorded based on the scale provided in [Table 7-3](#). The severity of all AEs/SAEs should be recorded on the appropriate eCRF page. Adverse events are graded as Grade 1, 2, 3, 4, or 5 corresponding, respectively, to a severity of mild, moderate, severe, life-threatening, or death.

Table 7-3 Adverse Event Severity

Severity	Definition
Grade 1 (Mild)	No limitation of usual activities.
Grade 2 (Moderate)	Some limitation of usual activities.
Grade 3 (Severe)	Inability to carry out usual activities.
Grade 4 (Life-threatening)	Immediate risk of death.
Grade 5 (Death related to an AE)	Death

7.23.4 Relatedness of Adverse Events and Serious Adverse Events

Relationship of an AE or SAE to investigational product, device, device surgical procedure, or IT administration process is to be determined by the Investigator based on the definitions in [Table 7-4](#):

Table 7-4 Adverse Event Relatedness

Relationship to Product(s)	Definition
Not Related	Unrelated to study drug, device, device surgical procedure, or IT administration process..
Possibly Related	A clinical event or laboratory abnormality with a reasonable time sequence to administration of study drug, device, device surgical procedure, or IT administration process but which could also be explained by concurrent disease or other drugs or chemicals.
Probably Related	A clinical event or laboratory abnormality with a reasonable time sequence to administration of study drug, device, device surgical procedure, or IT administration process unlikely to be attributable to concurrent disease or other drugs and chemicals and which follows a clinically reasonable response on de-challenge. The association of the clinical event or laboratory abnormality must also have some biologic plausibility, at least on theoretical grounds.
Definitely Related	
The event follows a reasonable temporal sequence from administration of the medication, device, device surgical procedure, or IT administration process follows a known or suspected response pattern to the medication, is confirmed by improvement upon stopping the medication (dechallenge) and reappears upon repeated exposure (rechallenge).
 
Note that this is not to be construed as requiring re-exposure of the patient to study drug; however, the determination of definitely related can only be used when recurrence of event is observed.

7.23.5 Procedures for Recording and Reporting Adverse Events

7.23.5.1 Reporting Serious Adverse Events Related to Study Procedures

Any SAE regardless of relationship to investigational product, device, device surgical procedure, or IT administration process that occurs in a patient after informed consent (and assent if applicable) should be recorded by the clinical site on an SAE form that is to be transmitted to the Shire HGT Medical Monitor and to the Shire Pharmacovigilance and Risk Management Department at the contact number provided below. The SAE must be completely described on the patient's eCRF, including the judgment of the Investigator as to the relationship of the SAE to the study procedure. The Investigator will promptly supply all information identified and requested by the Sponsor (and/or contract research organization [CRO]) regarding the SAE as to the relationship of the SAE to study drug, device, or procedure.

The SAE form must be completed and FAXED or scanned and EMAILED (PDF sent by e-mail) within 24 hours of the Investigator's learning of the event to:

Shire Pharmacovigilance and Risk Management Department:

International FAX: [REDACTED] **United Kingdom OR**

United States FAX: [REDACTED]

Email: [REDACTED]

AND

Shire HGT Medical Monitor:

FAX: [REDACTED] **(United States)**

The Investigator may also call the Medical Monitor directly (optional):

Shire HGT Medical Monitor: [REDACTED] **MD**

[REDACTED]

Shire HGT

Work: [REDACTED]

Cell: [REDACTED] **(24 hour access)**

Email: [REDACTED]

AND

Clinical Project Manager CC'd: [REDACTED]

Any follow-up information must also be completed on an SAE form and faxed or scanned to the same numbers or e-mail address listed above.

In the event of a severe and unexpected, fatal, or life-threatening SAE, the clinical site must contact the Shire HGT Medical Monitor by telephone; this is in addition to completing and transmitting the SAE form as stated above. The following provides contact information for the Shire HGT Medical Monitor.

If an SAE is assessed as severe and unexpected, or life-threatening, contact:

[REDACTED] **MD**

[REDACTED]

Shire Human Genetic Therapies, Inc.

[name]

[name]

Telephone: [REDACTED]

Fax: [REDACTED] **(United States)**

Mobile: [REDACTED] **(24-hour access)**

[REDACTED]

The Investigator must promptly report all required information to the Institutional Review Board (IRB)/Independent Ethics Committee (IEC). It is the responsibility of the Sponsor to ensure that each Investigator receives a copy of any CIOMS I/MedWatch report that has been submitted to the appropriate regulatory agencies notifying them of an unexpected related SAE. The Investigator or Sponsor must ensure that the IRB/IEC receives a copy of the report and that a copy is also filed within their study files. In addition, the Sponsor will also notify the Investigators and IRBs/IECs of all deaths that occur during the study, irrespective of relationship to study medication

